4.2 Inclusion Criteria

A subject must meet all of the following inclusion criteria to be eligible for participation in the study:

- 1. Is a male or female \geq 60 years of age
- 2. Can understand the nature of the trial and protocol requirements and provide written informed consent.

If the subject is deemed not competent to provide informed consent, the following requirements for consent must be met:

- a. The subject's legally acceptable representative (LAR) (or study partner/caregiver, if local regulations allow) must provide written informed consent
- b. The subject must provide written (if capable) informed assent
- 3. Subject requires some or complete assistance with one or more of the following:
 - a. Instrumental activities of daily living (communication, transportation, meal preparation, shopping, housework, managing medications, managing personal finances) OR
 - b. Basic activities of daily living (personal hygiene, dressing, eating, maintaining continence or transferring)
- 4. Meets clinical criteria for at least one of the following disorders, with or without cerebrovascular disease (CVD):
 - a. Parkinson's disease with or without dementia as defined by the Movement Disorder Society's Task Force (Appendix B)
 - b. Dementia with Lewy bodies (DLB) (Appendix C)
 - c. All-cause dementia, possible or probable Alzheimer's disease (AD) (Appendix A)
 - d. Frontotemporal degeneration spectrum disorders, including possible or probable:
 - i. Behavioral variant frontotemporal dementia (Appendix D)
 - ii. Progressive supranuclear palsy (Appendix E)
 - iii. Corticobasal degeneration (Appendix F)

Study: ACP-103-046 Clinical Study Protocol Amendment 7 Date: 5 March 2021

> e. Vascular dementia, including post-stroke dementia, multi-infarct dementia and/or subcortical ischemic vascular dementia (SIVD) (Appendix G)

- 5. Has an MMSE score ≥6 at Visit 1 (Screening) and Visit 2 (Baseline)
- 6. Has neuropsychiatric symptoms severe enough to warrant treatment with an antipsychotic agent, as evidenced by the Neuropsychiatric Inventory (NPI) score (Frequency×Severity) ≥4 on at least one of the following domains at Visit 1 (Screening) and Visit 2 (Baseline) (the domains at Screening and Baseline can be different):
 - a. Domain A Delusions; OR
 - b. Domain B Hallucinations: OR
 - c. Domain D Depression/Dysphoria; OR
 - d. Domain G Apathy/Indifference; OR
 - e. Domain H Disinhibition; OR
 - f. Domain I Irritability/Lability; OR
 - g. Domain K Sleep

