- 12. Has a heart rate <50 beats per minute. If bradycardia is secondary to iatrogenic or treatable causes and these causes are treated, a heart rate assessment can be repeated during the screening period.
- 13. Has a clinically significant CNS abnormality that is most likely contributing to the dementia or findings on MRI or CT including:
 - a. intracranial mass lesion (including but not limited to meningioma [>1 cm³ with evidence of peritumoral edema] or glioma)
 - b. vascular malformation

- c. intracranial aneurysm >4 points by PHASES score (Appendix L)
- d. evidence of >4 hemosiderin deposits (definite microhemorrhage or superficial siderosis)
- 14. Has clinically significant neuroimaging or laboratory abnormalities during Screening that in the judgment of the Investigator would jeopardize the safe participation of the subject in the study. In consultation with the Medical Monitor, these subjects may be rescreened after appropriate treatment of their medical condition.
- 15. Has major surgery planned during the screening through end of the treatment or follow-up periods
- 16. Requires treatment with a medication or other substance that is prohibited by the protocol
- 17. Has a body mass index (BMI) $<18.5 \text{ kg/m}^2$ or known unintentional clinically significant weight loss (i.e., $\ge 7\%$) over past 6 months
- 18. The urine drug screen result at Visit 1 (Screening) indicates the presence of amphetamine/methamphetamine, barbiturates, cocaine, or phencyclidine (PCP). Subjects who test positive for amphetamines may be retested during Screening if they agree to abstain from the medication for the length of their participation in the study and if abstinence from medication usage is achieved at least 7 days prior to Visit 2 (Baseline). The repeat Screening test must be negative for them to participate in the study. The presence of benzodiazepines, marijuana (THC), or opiates does not necessarily exclude the subject from the study.
- 19. Is suicidal at Screening or Baseline as defined below:
 - a. If the subject can complete the Columbia Suicide Severity Rating Scale (C-SSRS), he or she must not be actively suicidal at Visit 1 (Screening) or Visit 2 (Baseline) (including, an answer of "yes" to C-SSRS questions 4 or 5 [current or over the last 6 months]) and must not have attempted suicide in the 2 years prior to Visit 1 (Screening); OR

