5.2.6 Columbia-Suicide Severity Rating Scale

The C-SSRS will be used to assess suicidal ideations and behaviors in subjects who are able to complete the assessment (subjects without dementia, defined as an MMSE≥25, and subjects with dementia who the Investigator has determined can complete the C-SSRS). The C-SSRS is assessed (when applicable) at Screening, Baseline, Weeks 1, 2, 4, 6, and Week 8/ET visits .

The C-SSRS monitors changes in suicidal thinking and behavior over time, in order to determine risk. Four constructs are measured: the severity of ideation, the intensity of ideation, behavior, and lethality.

For subjects who are able to complete the assessment, the Baseline/Screening version will be administered at Screening, and the Since Last Visit version will be administered at subsequent visits. The C-SSRS results for each subject should be reviewed by the Investigator at each visit. If at any time the C-SSRS results for a given subject reveal potential suicidality, then the Investigator should assess the clinical significance of such results. If a clinically significant risk of suicidality is identified for a subject, then the Investigator should discontinue the subject and implement appropriate treatment.

There are 5 questions about suicidal ideation, representing 5 types of suicidal ideation: wish to be dead; non-specific active suicidal thoughts; active suicidal ideation with any methods (not plan) without intent to act; active suicidal ideation with some intent to act, without specific plan; active suicidal ideation with specific plan and intent. If a subject answers "yes" to any of these 5 questions, this subject will be counted as having suicidal ideation.

There are 5 questions about suicidal behavior, representing 5 types of suicidal behavior: preparatory acts or behavior; aborted attempt; interrupted attempt; actual attempt; suicide. If a subject answers "yes" to any of these 5 questions, this subject will be counted as having suicidal behavior.

Missing C-SSRS item scores will not be imputed.

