8.2 Disease Characteristics

Disease characteristics at Baseline will be summarized for the Randomized, Safety, and Full Analysis sets using descriptive statistics. MMSE total score, CGI-S, EQ-5D-5L VAS, SDI total score, and ESRS-A total score will be presented as continuous variables. CGI-S will be presented as a categorical variable using categories of 1 to 7, and MMSE total score will be

presented as a categorical variable using categories of ≤10, 11 to 17, 18 to 24, and 25 to 30. The number and percentage of subjects reporting suicidal ideation and suicidal behavior within the past 6 months and lifetime will be tabulated (for those subjects assessed with C-SSRS), and number and percentage of subjects reporting suicidality within the past 3 months and lifetime will be tabulated (for those subjects assessed with the GCAS).

Neuropsychiatric history will be summarized descriptively for continuous and categorical variables. Informed consent date will be used as the reference date when calculating duration of disease variables.

For both the Disease Characteristics and Neuropsychiatric History, summaries by region will be presented using the Safety Analysis Set.

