14.3.9 Suicidality

14.3.9.1 C-SSRS

The C-SSRS will be administered if the subject, in the Investigator's judgement, is able to reliably complete it. Otherwise, the GCAS will be administered and used thereafter in the study.

The event counts and the number and percentage of subjects reporting any post-Baseline suicidal ideation (wish to be dead; non-specific active suicidal thoughts; active suicidal ideation with any methods (not plan) without intent to act; active suicidal ideation with some intent to act, without specific plan; active suicidal ideation with specific plan and intent), suicidal behavior (preparatory acts or behavior; aborted attempt; interrupted attempt; actual attempt; suicide), or suicidality (any suicidal ideation or behavior) will be tabulated.

The event counts and the number and percentage of subjects reporting any post-Baseline non-suicidal self-injurious behavior will also be tabulated.

For calculating the percentages, the denominator will be the number of subjects with at least one post-Baseline C-SSRS assessment within each treatment group.

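### The planned C-SSRS table has no pre-dose reference, so persisting lower-level ideation is counted together with new or worsened ideation

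*SAP*

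**What the plan says.** SAP 14.3.9.1 presents "The event counts and the number and percentage of subjects reporting any post-Baseline suicidal ideation", suicidal behavior, and suicidality (either of these). For the percentages, "the denominator will be the number of subjects with at least one post-Baseline C-SSRS assessment within each treatment group". SAP 5.2.6 lists five ideation types in rising order, and after a yes to any of them "this subject will be counted as having suicidal ideation". Protocol 9.5.3 is no finer.

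At entry, exclusion 19a (Protocol 4.3) bars subjects who are actively suicidal. What it goes on to name is a yes to "C-SSRS questions 4 or 5 [current or over the last 6 months]) and must not have attempted suicide" in the 2 years before Visit 1. Exclusion 19c adds active suicidality in the Investigator's judgment. One of the NPI domains that can qualify a subject alone is "Domain D Depression/Dysphoria" (Protocol 4.2).

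Pre-dose data are collected. The Baseline/Screening form is used at Visit 1, and "the Since Last Visit version will be administered at subsequent visits", which includes Visit 2. SAP 8.2 describes the history separately: "The number and percentage of subjects reporting suicidal ideation and suicidal behavior within the past 6 months and lifetime will be tabulated". No planned table crosses it with the post-Baseline result.

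**The concern.** The C-SSRS is a named exploratory safety endpoint, and the question put to it is whether suicidality appears or gets worse on pimavanserin compared with placebo. A count of any post-Baseline ideation answers a different question, namely how many subjects have ideation at any time after dosing, including those who had it before.

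The SAP uses a pre-dose reference for most other safety data. Pre-dose findings on Day 1 are not TEAEs (14.1). Laboratory values get shift tables and a PCI summary by Baseline status (14.3.5.2, 14.3.5.3). Blood pressure and pulse PCI values need a change from Baseline as well as a threshold (Table 5). ECG interpretations get shift tables (14.3.7.2.3). GCAS ratings of 3 or 4 are close to emergent already, because entry bars them. C-SSRS ideation has no such reference. At stake is a safety table that looks more reassuring than the same data would if new and persisting ideation were separated.

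**Working it through.** **The plan's own figures.** The documents give no rate or precision for the C-SSRS. The only design figures are the probabilities of seeing at least one AE in 375 subjects. 1 − (1 − p)^375 gives 0.9769, 0.9965 and 0.99949 at p = 1.0%, 1.5% and 2.0%, matching 0.977, 0.997 and 0.999. This point does not affect them.

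**Who can carry ideation into the trial.** I take the C-SSRS question numbers to follow the order of types in SAP 5.2.6. Types 4 and 5 (current or last 6 months) are then barred by name. Types 2 and 3 are described there as active thoughts or ideation, so the bar on active suicidality may reach them when current. Type 1 is not active ideation on that list and is not named. Recent attempts are barred; preparatory, aborted and interrupted acts are not named.

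**Illustration (all values assumed).** Let b be the share with ideation before dosing, q the share of those who report it again, and new ideation in the rest 1% on placebo and 3% on pimavanserin (ratio 3.0, difference 2.0 points).

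Planned row = b × q + (1 − b) × new rate. For b = 5%, q = 0.5:
- placebo: 0.05 × 0.5 + 0.95 × 0.01 = 3.45%
- pimavanserin: 0.05 × 0.5 + 0.95 × 0.03 = 5.35%

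| b | q | Placebo vs pimavanserin | Ratio | Difference (points) |
|---|---|---|---|---|
| 0 | – | 1.00% vs 3.00% | 3.00 | 2.00 |
| 2% | 0.5 | 1.98% vs 3.94% | 1.99 | 1.96 |
| 2% | 0.8 | 2.58% vs 4.54% | 1.76 | 1.96 |
| 5% | 0.5 | 3.45% vs 5.35% | 1.55 | 1.90 |
| 5% | 0.8 | 4.95% vs 6.85% | 1.38 | 1.90 |
| 10% | 0.5 | 5.90% vs 7.70% | 1.31 | 1.80 |
| 10% | 0.8 | 8.90% vs 10.70% | 1.20 | 1.80 |

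**Noise around the difference.** Assume 150 C-SSRS subjects per arm, b = 5%, q = 0.5.
- Planned row: SE = √[(0.0345 × 0.9655 + 0.0535 × 0.9465)/150] = 2.37 points.
- New onset among the 142.5 per arm without prior ideation: SE = √[(0.01 × 0.99 + 0.03 × 0.97)/142.5] = 1.65 points. The planned row's SE is 43% larger.
- New-or-worsened count over all 150, as proposed below, if nobody with prior ideation worsens: 0.95 × 1% = 0.95% vs 0.95 × 3% = 2.85%. The ratio is 3.0 and the difference 1.90 points, with SE = √[(0.0095 × 0.9905 + 0.0285 × 0.9715)/150] = 1.57 points.

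In subjects, the planned row holds about 5.2 vs 8.0 (150 × 3.45% and 150 × 5.35%). Of these, 150 × 5% × 0.5 = 3.75 in each arm are persisting cases, and about 1.4 vs 4.3 are new.

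**The case against.** The case for leaving the table alone has several parts.

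- **Rows by type.** SAP 14.3.9.1 lists every ideation and behavior type inside the tabulation sentence, and table layouts are in a separate document (SAP 1). A row per type may be intended. A reader might infer that escalation to intent or plan is hidden in the any-ideation count. The documents do not support that: with such rows, types 4 and 5 would be visible, and new relative to the prior 6 months because entry bars them. What stands is that the text does not commit to those rows, and that even with them a move from type 1 to type 3 could not be seen.
- **Entry.** A reader might infer that types 1 to 3 are all freely admitted. That is too strong, because the wording on active suicidality, 19c and exclusion 24 (danger to self) may keep out current types 2 and 3. What stands is type 1.
- **Other routes.** An AE start date includes sustained worsening (Protocol 7.2.2.1). TEAEs, serious TEAEs and those leading to discontinuation are tabulated by arm, and all data are listed (SAP 5). This is real cover, but it depends on the Investigator reporting an AE, and it yields no planned C-SSRS count by arm.
- **No inference is planned.** Section 14.3.9.1 plans no ratio, interval or test, and the tests added in SAP 19 are for efficacy and secondary safety variables. Loss of precision or power therefore harms no planned output. This objection stands and limits the point to how a descriptive table reads.

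**Conclusion.** The point holds in a limited form. The planned table mixes persisting with new or worsened ideation, and no planned table shows movement among types 1 to 3. A reader might go further and call the comparison biased. It is not: randomization balances prior ideation in expectation, so the effect is dilution, and with no pre-dose ideation the two counts coincide.

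The size cannot be known from the documents. Under the assumed rates a new-onset ratio of 3.0 shows as 1.20 to 1.99 across 2% to 10% pre-dose ideation and 50% to 80% persistence. The risk difference stays within 1.80 to 1.96 points of the assumed 2.0. These figures rest on equal prior ideation and equal persistence in both arms.

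Priority is minor. The endpoint is exploratory and descriptive, and the SAP carries out what Protocol 9.5.3 describes. The addition is still worth making because it is cheap and fixes the definition of emergent ideation before the final counts are seen.

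**What to change.** Keep the planned rows in SAP 14.3.9.1 and add, by arm:

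1. A shift table of highest pre-dose ideation type (Screening past 6 months and Visit 2 combined) against highest post-Baseline type, with a count of new or worsened ideation. The denominator is subjects with both a pre-dose and a post-Baseline C-SSRS. Repeat it with the Visit 2 since-last-visit result alone as the reference. The combined reference avoids relying on the short Screening-to-Baseline interval; the Visit 2 reference catches ideation that had resolved by Baseline and then returned at the same level.
2. An explicit row for any post-Baseline type 4 or 5 ideation.
3. Emergent suicidal behavior, with numerator and denominator both limited to subjects with no behavior in the 6 months before dosing and at least one post-Baseline C-SSRS.

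The cost is a few lines of SAP text and some table programming, with no new data collection. The small downside is that subjects without a pre-dose C-SSRS drop out of items 1 and 3; their number should be footnoted.

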14.3.9.2 GCAS

The number and percentage of subjects within each GCAS rating will be summarized using the clinician rating. The number and percentage of subjects reporting any post-Baseline rating of 3 or 4 will be tabulated. For these analyses, the denominator for calculating percentages is the number of subjects with at least one post-Baseline GCAS assessment within each treatment group.

Subject and study partner/caregiver ratings will not be summarized but will be included in data listings.

15 CLINICAL PHARMACOKINETIC AND PHARMACODYNAMIC ANALYSES

Not applicable.

16 UNBLINDED INTERIM ANALYSES

16.1 General Procedure

One or more unblinded IAs of data from subjects who have exited the study (completed with or without enrolling into the open-label extension, or terminated early) may be conducted in order to support safety and efficacy evaluations for regulatory submissions. Subjects who have exited the study will only be unblinded and analyzed if all other subjects in the same randomization block have also exited the study.

The analyses planned for an unblinded IA will align with the purpose of the regulatory submission. Study subjects, study partners/caregivers, Investigators, raters, and site personnel will remain blinded to subject treatment assignments until all subjects have completed the study and the clinical database is locked. The distribution of unblinded subject's treatment assignments within Acadia will be restricted. Further details regarding the restricted distribution of treatment assignments, IA results, and unblinding procedures will be specified in an IA Unblinding Plan.

16.2 Interim Analysis 1

The database lock for the first interim analysis (IA-1) occurred on December 13, 2019 (under version 1 of the SAP), and included data from 288 subjects whose last visit occurred on or before December 2, 2019. Data from these subjects may be used as a pre COVID-19

comparison group for selected safety and efficacy endpoints, in order to assess the potential impact of COVID-19 on the final study results.

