3.6 Coronavirus Disease 2019

In March, 2020, the emerging coronavirus disease 2019 (COVID-19) pandemic resulted in implementation of urgent safety measures designed to ensure subject safety. Mechanisms to record information on the potential impact of the COVID-19 pandemic on data itself, as well as data collection and integrity, were implemented (as detailed in the Data Management Plan [DMP] Appendix B). Recruitment efforts into ACP-103-046, and roll-overs into the open-label extension study (ACP-103-047), were paused. The impact of COVID-19 on statistical analysis is discussed in each of the relevant sections of this SAP.

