7 PROTOCOL DEVIATIONS

Protocol deviations will be reviewed periodically over the course of the study. The review process, definition of the deviation categories, and the classification of a deviation as major

or minor will be detailed in the Protocol Deviation Management Plan. For subjects who were not included in IA-1, protocol deviations will also be assessed with respect to relationship to COVID-19.

For randomized subjects, a summary of the number and percentage of subjects with major protocol deviations for each deviation category will be presented in three ways: all protocol deviations, COVID-19 related protocol deviations, and non COVID-19 related protocol deviations.

Similarly, three data listings of major protocol deviations will be provided: All deviations, COVID-19 related protocol deviations, and non COVID-19 related protocol deviations. Additionally, a data listing of all minor COVID-19 related protocol deviations will be provided.

In order to assess the potential impact of COVID-19 on missed visits, the proportion of missed visits will be tabulated by treatment arm for the Safety analysis set, computed as the number of total number missed visits divided by the total number of expected visits. This will be tabulated separately for IA-1 subjects, and subjects enrolled after IA-1, as a proxy for pre- and post-COVID-19 analyses.

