14.1.2 Assessment of the Impact of COVID-19 on Adverse Events

The relationship of selected AEs to COVID-19 will be assessed by investigator as detailed in the DMP Appendix B, for those subjects who were not unblinded as part of the first interim analysis. Each of the primary safety analyses described in Section 14.1.1 will be additionally summarized by relationship to COVID-19 (Not related to COVID-19 vs. Related to COVID-19).

Both the Not related to COVID-19 and the Related to COVID-19 AE tables will be summarized using 2 sets of subjects: all subjects in the Safety analysis set, and subjects in the Safety analysis set that were not included in IA-1, as a proxy for pre- and post-COVID-19 analyses.

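### The SAP's pre/post-COVID-19 proxy is tied to IA-1 (last visit by 2 December 2019), not to the March 2020 disruption, so pre-pandemic visits and subjects are counted on the post-COVID side of two supportive tables

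*SAP*

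**What the plan says.** SAP 3.6 dates the disruption: "In March, 2020, the emerging coronavirus disease 2019 (COVID-19) pandemic resulted in implementation of urgent safety measures". It gives no day in March.

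SAP 16.2 describes IA-1. It states that "The database lock for the first interim analysis (IA-1) occurred on December 13, 2019" and that the analysis "included data from 288 subjects whose last visit occurred on or before December 2, 2019". It continues: "Data from these subjects may be used as a pre COVID-19" comparison group for selected endpoints. SAP 16.1 adds that exited subjects "will only be unblinded and analyzed if all other subjects in the same randomization block have also exited the study".

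Two sections then build tables on IA-1 status:

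- SAP 7, proportion of missed visits by arm in the Safety Analysis Set: "This will be tabulated separately for IA-1 subjects, and subjects enrolled after IA-1, as a proxy for pre- and post-COVID-19 analyses".
- SAP 14.1.2, adverse event tables by relationship to COVID-19. These are produced for the whole Safety Analysis Set and again for "subjects in the Safety analysis set that were not included in IA-1, as a proxy for pre- and post-COVID-19 analyses".

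No section of the SAP splits data by calendar date.

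**The concern.** IA-1 status reflects when an interim database was closed. It marks the start of the pandemic only if few subjects were in the study between the two dates, and the SAP neither says so nor mentions the gap.

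The missed-visit table has the stated purpose of showing the impact of COVID-19 on attendance. If its later column holds visits made before any restriction existed, the column understates what happened once restrictions applied. In the adverse event tables, subjects who had finished before March 2020 can hardly contribute a COVID-related event, yet they sit in the denominator of the set offered as the post-COVID proxy. Both effects point toward little apparent impact, which is the unhelpful direction for a check meant to detect impact.

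A proxy is reasonable when the real variable is missing. Here it is not. SAP 5.3 derives study day from assessment and first-dose dates, and SAP 14.1.1 lists onset dates. COVID-19 handling entered the SAP in version 2.0 of 26 May 2020, when the March date was already known.

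**Working it through.** The plan gives no figure of its own on this point, so the check is date arithmetic.

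**Inputs.** IA-1 cut-off 2 December 2019 and lock 13 December 2019 (SAP 16.2). Disruption in March 2020, day not given, so 1 to 31 March is used (SAP 3.6). Target study days 8, 15, 29, 43 and 57, with Day 1 the first dose (SAP Table 2). Planned enrolment about 750 (SAP 3.5). First dose is taken as the randomisation date.

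**1. Length of the gap.**
- Onset 1 March: 3 December to 29 February = 29 + 31 + 29 = 89 days.
- Onset 31 March: 89 + 30 = 119 days.

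**2. Missed-visit table (SAP 7).** The later column is defined by enrolment after IA-1, so the exit window in step 1 does not apply directly. Target date = first dose + target day − 1.
- A subject starting on 14 December 2019, the day after the lock, has Week 8 on 14 December + 56 days = 8 February 2020. All five post-Baseline visits precede March, yet all count as post-COVID.
- A completer has every treatment visit before 1 March if randomised by 29 February − 56 days = 4 January 2020. That is 22 days after the lock, or 33 days after the cut-off. For onset on 31 March the limit is 3 February 2020 (52 or 63 days).
- A subject starting on 1 February 2020 has target dates of 8, 15 and 29 February and 14 and 28 March. With onset on 1 March, three of the five visits are mislabelled.

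**3. Subjects in neither column (SAP 7).** 2 December − 56 days = 7 October 2019. A completer randomised from 8 October 2019 has a Week 8 target after the cut-off and so is not in IA-1. If that subject was also randomised before IA-1, the literal wording places the subject in neither column. The randomisation window is 24 + 30 + 2 = 56 days if IA-1 means the cut-off date, or 67 days if it means the lock. The SAP does not say which. The block rule in SAP 16.1 can also hold out subjects who exited on or before 2 December.

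**4. Adverse event tables (SAP 14.1.2).** Every subject whose last visit fell in the gap of step 1 is in the non-IA-1 set. If such subjects make up a fraction f of that set and have no COVID-related events, then

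displayed rate = (1 − f) × rate among the other non-IA-1 subjects.

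The documents give no accrual or exit rate, so f cannot be calculated. For illustration only, take the planned total (750 − 288 = 462 outside IA-1) and assume 10 to 40 exits per month:
- low: 10 × 2.9 months = 29 subjects, 29/462 = 6%, factor 0.94;
- high: 40 × 3.9 months = 156 subjects, 156/462 = 34%, factor 0.66.

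The width of this range reflects the assumption and is not a finding about the trial.

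**The case against.** The strongest reply has four parts.

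- *The SAP calls the split a proxy, and its use under SAP 16.2 is optional.* True, so this is a weakness and not a contradiction. The IA-1 group is also sound as a pre-COVID group, because all 288 subjects finished before March 2020. The trouble lies on the other side of the split.
- *IA-1 membership is also the boundary of data capture.* This stands and shapes the fix. COVID-19 related terminations and screen failures (SAP 6), deviations (SAP 7), medications (SAP 10.4) and attribution of adverse events (SAP 14.1.2) are collected or assessed only for subjects outside IA-1. A reader might infer that IA-1 membership should be dropped from all COVID-19 summaries. That would detach those tables from the population in which the variable exists.
- *The adverse event tables do not contrast IA-1 with non-IA-1.* Correct. SAP 14.1.2 shows the whole Safety Analysis Set and the non-IA-1 subset. A reader might infer that a pre/post difference is shrunk by a definite percentage. No such difference is estimated there, and any percentage rests on an assumed exit rate. What remains is the enlarged denominator.
- *COVID-19 effects are also captured directly.* True. Investigator attribution covers several of the same questions, so these tables are not the SAP's only means of judging impact.

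None of this explains why the visit table should use a December boundary when visit dates are available.

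**Conclusion.** The point holds as a minor one. The IA-1 boundary precedes the disruption that the SAP itself dates by 89 to 119 days. Following the plan as written labels some pre-pandemic visits as post-COVID, leaves some subjects out of the missed-visit table, and puts subjects who had already finished into the non-IA-1 adverse event denominator. SAP 7 and 14.1.2 also define their later group differently, so the two tables do not describe the same people.

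The direction is toward less apparent COVID-19 impact, on the assumption that pre-March visits and subjects resemble those in IA-1. The number affected is unknown.

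Two stronger readings are not supported. A reader might infer that about three months of exiting subjects are misclassified in every COVID-19 table. That window fits the non-IA-1 set of SAP 14.1.2 and not the enrolment-based column of SAP 7. A reader might also infer that the main safety results are compromised. They are not: the TEAE tables of SAP 14.1.1 and the MMRM analyses do not use the split. The affected tables are descriptive, with no test or decision rule attached.

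**What to change.** 1. In SAP 3.6, state one reference date in March 2020 for the start of the urgent safety measures.
2. In SAP 7, class every expected visit of all Safety Analysis Set subjects by its target date (first dose + target day − 1), before versus on or after the reference date. A missed visit has no actual date, so the target date is the right one. Every subject then contributes, and the group in neither column disappears.
3. In SAP 14.1.2, replace or supplement the non-IA-1 proxy with a split by adverse event onset date, or with three subject groups: finished before the reference date, in study across it, randomised after it. If onset date is used, take as the later denominator the subjects with any time in study on or after the reference date, and handle partial dates as in SAP 5.4.3.
4. Use the same groups for any optional comparison under SAP 16.2.
5. Keep IA-1 membership as the boundary for summaries that rely on investigator attribution to COVID-19, and say that this is the reason.

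Cost: one derived flag, a few lines of SAP text and slightly more tabulation. No new data are needed.
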